## 6.6 ANALYSIS OF HEALTH CARE RESOURCE UTILIZATION

Descriptive statistics will be used to tabulate HCRU during the post-index period (Appendix 1, Analysis Table 18). Characteristics will consist of items such as whether a hospitalization occurred; primary reason for the hospitalization; location (ward) of the hospitalization; use of a mechanical ventilator; days between isavuconazole initiation and hospital admission and discharge; and length of stay, which will be computed as the discharge date minus the admission date + 1.

Additionally, HCRU characteristics will be summarized for health care professional visits or referrals. Characteristics will consist of items such as the type and number of health care professional visits or referrals, primary reason for visit or referral, type of health care professional, and days between isavuconazole initiation and first visit or referral (Appendix 1, Analysis Table 19).

Potential analyses of subgroups may be performed but have not been defined explicitly in Appendix 1.

PFIZER CONFIDENTIAL

CT24-WI-GL03-RF03 1.0 *Non-Interventional Statistical Analysis Plan For Secondary Data Collection*  
Study 16-Sep-2020  
Page 17 of 19

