9.2. Setting

9.2.1. Study Sites

A feasibility assessment was conducted, and a total of 22 sites meeting the study criteria were identified: 6 in Germany, 5 in Italy, 5 in Spain, 4 in the UK, and 2 in France. All sites are hospital-based facilities and had access to eligible medical records of patients treated within oncology, hematology, and/or transplantation wards and ICUs. During this feasibility assessment, sites were evaluated on the following parameters, to determine their suitability for participation:

- Number of eligible patients treated with isavuconazole for either invasive aspergillosis or mucormycosis.
- Location of medical records and continuity of data across wards and staff resources, to be able to abstract the required data.
- Frequency and availability of follow-up data.

The total number of sites who participate in the study may differ from the anticipated number (22), depending on a site's interest and the availability of its staff (considering the COVID-19 pandemic), and access to eligible medical records. The sites will be hospital based; thus, the patient population will consist of those who were either hospitalized or attending a hospital at the initiation of isavuconazole therapy. As invasive aspergillosis and mucormycosis are rare fungal infections, we expect that the pool of potential patients across sites will be small. The total number of patients eligible patient records to which the sites have access was estimated to be about 583.

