9.4.6. Health Care Resource Utilization

Category	Variable	Timepoint
Inpatient hospitalizations (including specialty wards, ICU, ER, general medicine ward, or other)	
Inpatient hospitalization occurring after index treatment initiation
 
 • Yes; • No; • Unknown. 
Primary reason for hospitalization:
 
 • Invasive aspergillosis or mucormycosis disease monitoring; • Other disease monitoring; • AE related to invasive aspergillosis or mucormycosis; • Other (specify); • Unknown. 
Location for inpatient hospitalization:
 
 • Oncology ward; • Hematology ward; • Transplantation ward; • ICU; • ER; • General medicine ward; • Other ward (specify); • Unknown. 
Use of a mechanical ventilator:
 
 • Yes; • No; • Unknown. 	Post-index period

Category	Variable	Timepoint
	
Discharge date (DD MMM YYYY)
 
Discharge location (if applicable):
 
 • Transferred to another ward for inpatient care; • Discharged to home or self-care (routine discharge); • Discharged to long term care facility/hospice; • Not applicable; • Other (specify); • Unknown. 	
Outpatient visits (not associated with a hospital stay)	
Outpatient visit/referral occurring after index treatment initiation:
 
 • Yes; • No; • Unknown. 	Post-index period
	
Health care professional visit or referral:
 
 • Primary care visit (general practitioner); • Secondary care visit (specialist); • Secondary care referral (specialist); • ER visit. 	
	
Primary reason for visit/referral:
 
 • Planned visit/referral for invasive aspergillosis or mucormycosis disease monitoring; • Unplanned visit/referral for invasive aspergillosis or mucormycosis disease monitoring; • Planned visit/referral for other disease monitoring; • Unplanned visit/referral for other disease monitoring; • Unplanned visit/referral for AE related to invasive aspergillosis or mucormycosis; • Other; • Unknown. 	
	
Type of health care professional:
 
 • Infectious disease specialist; 	

Category	Variable	Timepoint

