9.9.2.2. Analysis Plan for Secondary Objectives

Basic summaries of site and patient counts included in the study will be produced. Patients will be characterized by fungal disease type (invasive aspergillosis or mucormycosis) at the time of isavuconazole initiation, in terms of demographics, disease characteristics, medical history, treatment history, prognostic factors, and other factors which may be predictive of clinical outcome.

For isavuconazole treatment patterns, descriptive statistics will be used to summarize details of isavuconazole administration (eg, location, therapy duration, loading dose and frequency, and maintenance dose and frequency), modifications to index therapy, details of therapeutic drug monitoring (therapeutic drug monitoring [TDM], eg, assay type, outcome), discontinuation, switching, antibiotic use before and after index therapy, and concomitant medication.

Health care resource utilization during the post-index period will be reported at 6 weeks, 12 weeks, and 24 weeks after initiation of index therapy. HCRU will include counts and proportions of patients with inpatient visits, outpatient visits, ICU admissions and ER visits and use of mechanical ventilators. Reason for visits and duration of visits will be described. Inpatient LOS and ICU LOS will be derived using admission and discharge dates.

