**Figure 1 Overview of Study Periods and Examples of Eligible Cases**

### 4.2 STUDY PERIODS

[figure not shown]
The index event is defined as the first initiation of isavuconazole treatment for the invasive fungal infection. The index event serves as the point at which (1) a patient

PFIZER CONFIDENTIAL

qualifies for study inclusion, (2) patient follow-up begins, and (3) the patient becomes at risk for experiencing study outcomes. Study periods for data extraction and variable assessment are defined relative to the index event (Figure 1).

- **Eligibility period:** The index date must occur within the eligibility period, which is the timeframe wherein potentially eligible patients are identified for enrolment. *The dates comprising the eligibility period will be October 15, 2015 (date of isavuconazole approval by the EMA in the EU), to June 30, 2019. The end date of the eligibility period ensures that the latest date of isavuconazole initiation will occur at least 6 months before the end of December 2019 (after which point the medical records may contain data related to the COVID-19 pandemic, which is not of interest for this study). This definition will allow for a minimum of 6 months of follow-up from the date of isavuconazole initiation unless the patient dies or is lost to follow-up within this timeframe.*
- **Pre-index period:** *Baseline data on demographics and medical history will be collected based on all available information in medical records before the index event.*
- **Post-index period:** *The timeframe for follow-up data collection will begin one day post-index treatment initiation and end at the earliest of the following: 6 months after post-index treatment discontinuation, death, or loss to follow-up (Figure 1 and Figure 2). Key timepoints of interest for assessment of clinical response and safety will be at 6 weeks, 12 weeks, and 24 weeks after initiation of index treatment (Figure 2).*

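### The SAP's length-of-stay formula is not bounded to the post-index window, so stays ongoing at isavuconazole initiation are measured too long or left out, depending on how the form is read

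*SAP*

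**What the plan says.** - **Window.** SAP 6.6: "Descriptive statistics will be used to tabulate HCRU during the post-index period". SAP 4.2 sets the start of that period: "The timeframe for follow-up data collection will begin one day post-index treatment initiation".
- **Formula.** SAP 6.6 gives the only computational rule: "length of stay, which will be computed as the discharge date minus the admission date + 1". Protocol 9.9.2.2 says: "Inpatient LOS and ICU LOS will be derived using admission and discharge dates". It also sets reporting times: "Health care resource utilization during the post-index period will be reported at 6 weeks, 12 weeks, and 24 weeks after initiation of index therapy". SAP 6.6 does not repeat those times.
- **Who is in hospital at index.** Protocol 9.2.1: "the patient population will consist of those who were either hospitalized or attending a hospital at the initiation of isavuconazole therapy". SAP Table 1 likewise lists outpatient treatment after an inpatient start as a treatment pattern.
- **Which stays count.** The form item in Protocol 9.4.6 is "Inpatient hospitalization occurring after index treatment initiation". The HCRU outcome in SAP Table 1 is any documented inpatient stay.
- **Record structure.** Protocol 9.4.6 records a ward for each hospitalization and lists, among discharge locations, "Transferred to another ward for inpatient care". Protocol 9.11 expects inpatients to change wards during treatment.

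**The concern.** The formula measures a hospital stay from admission to discharge. The table it feeds is meant to describe use after isavuconazole started. The two agree only for stays that begin on or after the index date and end within follow-up. The plan expects part of the cohort to be in hospital already at the first dose, and it does not say whether that stay is included whole, cut at index or left out.

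The unit of analysis is also open. A record can close at a ward transfer, and separate ICU stay is required, so one hospital episode may appear as several records with no rule for combining them.

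At stake is whether the reported inpatient and ICU days describe the post-index period at all. Two analysts following the same SAP could report materially different numbers for the same patient.

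**Working it through.** **No figure to reproduce.** Neither document states a numerical length of stay, the share of patients in hospital at index, their pre-index days or the number of ward moves. All dates below are assumptions chosen to show the mechanism. Index day = 0.

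**Formulas**
- SAP 6.6: LOS = discharge − admission + 1.
- Truncated at index: LOS = discharge − max(admission, index) + 1.
- If admission precedes index by p days, the first exceeds the second by p days (p + 1 if counting starts on the day after index, as in SAP 4.2).

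**Effect of pre-index days, if the ongoing stay is included**

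| Pre-index days p | Discharge day | SAP formula | Truncated at index | Excess |
|---|---|---|---|---|
| 3 | 28 | 32 | 29 | 3/29 = 10% |
| 7 | 28 | 36 | 29 | 7/29 = 24% |
| 14 | 28 | 43 | 29 | 14/29 = 48% |
| 3 | 14 | 18 | 15 | 3/15 = 20% |
| 7 | 14 | 22 | 15 | 7/15 = 47% |
| 14 | 14 | 29 | 15 | 14/15 = 93% |

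**Effect of ward records, if they are summed.** Each contiguous record carries its own +1, so k records add k − 1 days. A stay from day 1 to day 28 is 28 days as one record, 29 as two, 30 as three and 31 as four.

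**Both together.** Admission day −10, ward to ICU day 5, ICU to ward day 12, discharge day 25:

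| Reading | Arithmetic | Days | Against 26 |
|---|---|---|---|
| Truncated at index | 25 − 0 + 1 | 26 | reference |
| Whole stay, SAP formula | 25 − (−10) + 1 | 36 | +10 (+38%) |
| Three ward records, summed | 16 + 8 + 14 | 38 | +12 (+46%) |
| Only records starting after index, summed | 8 + 14 | 22 | −4 (−15%) |

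Counted from the day after index, the reference is 25. If the form holds one record per hospital stay and only new admissions qualify, this episode contributes no days.

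**Upper bound.** The formula has no stop at the end of follow-up or at weeks 6, 12 and 24, so a stay crossing one of those points is not cut there. It also needs a discharge date, while the discharge locations in Protocol 9.4.6 include no explicit option for death. The plan's own benchmarks for death by day 42 are 19% (Protocol 7.2, aspergillosis) and 35% (Protocol 7.3, mucormycosis), so deaths in hospital are likely to be common enough to need a stated rule.

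**The case against.** The strongest reply is that the plan does not commit itself to either error. The form item can be read as new admissions only, in which case no pre-index day enters. Nothing says that ward records are added up. For a single whole stay, +1 is an ordinary inclusive-day count, and ICU stay reported on its own sums nothing. SAP 6.6 also tabulates days from initiation to admission and to discharge, which would show the two parts of an index stay recorded as one record. The table shells sit in an embedded file that was not available for this review and may settle the unit of analysis.

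Most of this stands, and it rules out several stronger readings that a reader might infer:
- **That the rule necessarily overstates stay.** The new-admissions reading understates it.
- **That transfer days are counted twice.** This depends on summing records, which the documents do not state, and the effect is only k − 1 days.
- **That the form lacks an admission date.** Its absence from the Protocol 9.4.6 table shows nothing: Protocol 9.4 calls the list non-exhaustive, and Protocol 9.9.2.2, Protocol 9.10 and SAP 6.6 all rely on admission dates.
- **That length of stay is the main HCRU quantity.** Protocol 9.9.2.2 lists it alongside counts and proportions of visits, ICU admissions and ventilator use.
- **That deaths have no end date at all.** Date of death is collected and follow-up ends at death; what is missing is the link to the formula.

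The reply does not rescue the formula. Excluding the ongoing stay discards real post-index days; including it without truncation adds days outside the window. The auxiliary intervals help a reader of one record, but they do not make the reported length-of-stay summary a post-index quantity.

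**Conclusion.** The point holds as a mismatch between a stated window and a stated formula. For patients admitted before the index date, post-index length of stay is wrong under either available reading: too long by the number of pre-index days if the ongoing stay is included, too short if it is excluded. The direction across the cohort cannot be determined from the documents.

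The size depends on quantities the documents do not give. Under the assumed dates, one patient's value is 22, 36 or 38 days against 26. The pre-index part can be large; the transfer part is small and conditional on summing ward records. Length of stay is secondary and descriptive, so mortality, response and safety are not affected. The correction is still worth making, because it is cheap and the plan otherwise leaves the result to the programmer.

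**What to change.** Add to SAP 6.6:

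1. The stay ongoing at index is included.
2. Contiguous ward records are merged into one hospital episode before any duration is computed.
3. Post-index length of stay runs from the later of admission and index date (or the day after index, to match SAP 4.2) to the earliest of discharge, death and end of follow-up. End of follow-up needs one definition: Protocol 9.3.1.3 includes December 31, 2019, and SAP 4.2 does not.
4. Where HCRU is reported at weeks 6, 12 and 24, stays are also truncated at those points.
5. Pre-index days of the index stay are reported separately, so nothing is lost.
6. ICU length of stay is derived from ICU records with one stated rule for transfer days.

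The cost is SAP wording and derivation code, using dates the plan already requires. Timing matters: Protocol 9.10 has the data capture system calculate durations and says dates will not be kept in the data set. The rule should be fixed before those durations are derived; afterwards, repair depends on which intervals were retained for each record.

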## 8 APPENDICES

### 8.1 APPENDIX 1: EXAMPLE ANALYSIS TABLES AND FIGURES

Please click on the Excel icon in the left column of this PDF to open up the tables.

PFIZER CONFIDENTIAL

CT24-WI-GL03-RF03 1.0 *Non-Interventional Statistical Analysis Plan For Secondary Data Collection*  
Study 16-Sep-2020  
Page 19 of 19
